1.0 Objectives

1.1 Study Objectives

1. To determine the degree of surgically induced astigmatism of femtosecond laser clear corneal incisions
2. To determine the post-operative mean reduction in keratometric astigmatism and uncorrected distance visual acuities in patients undergoing femtosecond laser-assisted cataract surgery with astigmatic keratotomy (AK)
3. To determine the role of corneal biomechanics (hysteresis) on AK calculations.
4. To develop a nomogram that may be utilized in determining location and arc length of AKs for femtosecond laser-assisted cataract surgery with astigmatic keratotomy

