3.0 Inclusion and Exclusion Criteria

3.1 Inclusion Criteria

- Age: ≥18 years of age
- Sex: male or female
- Patients who are planned to undergo femtosecond laser-assisted cataract surgery with astigmatic keratotomy at the Schein Ernst Mishra Eye clinic within the next 60 days of their cataract consultation visit. Subjects with planned single or bilateral cataract eye surgeries are eligible. Planned opposite eye surgery must be within 2-4 weeks of first cataract surgery.
- Fluent in written and spoken English

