7.2 Study Procedures

7.2.1 Visit 1 or Day 1 or Pre-test, etc. (format accordingly)

Pre-operative visit: Inclusion/exclusion criteria will be assessed. Consent will be obtained from eligible subjects who wish to participate in the study. Demographic and baseline characteristics will be recorded. Pre-operative biometry, refraction, and corneal hysteresis data will be collected.

7.2.2 Visit 2

Day of surgery: Data from the femtosecond laser will be collected, including the various laser parameters that are used to make the astigmatic keratotomies and clear corneal incisions.

7.2.3 Visit 3

Day of surgery for contralateral eye: Data from the femtosecond laser will be collected, including the various laser parameters that are used to make the astigmatic keratotomies and clear corneal incisions.

7.2.4 Visit 4 or post-operative month #1 visit (1 month after 2nd operative procedure)

Post-operative month 1 visit: One-month post-operative IOL master, autorefraction, manifest refraction, and uncorrected visual acuity will be collected.

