7.3 Duration of Participation

The individual subject will participate in the study from the time consent is obtained at their pre-operative visit, through their femtosecond laser-assisted cataract surgery with astigmatic keratotomy on both eyes, and until their one-month post-operative visit.

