8.3 Statistical methods

Eyes that do not obtain a final best-corrected visual acuity of 20/40 or better will be excluded from the final data analysis. Mean change in keratometric astigmatism will be determined by subtracting preoperative astigmatism from postoperative mean astigmatism. Vector analysis and double-angle plot will be used to analyze aggregate astigmatism. We will require assistance from a statistician.

A sub-group analysis will likely include patients that had prior refractive surgery (i.e. LASIK).

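### Objective 1 asks for the astigmatism induced by the clear corneal incision, but no stated analysis separates it from the AK effect

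*Combined protocol and SAP*

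**What the plan says.** Section 1.1 lists as its first objective "To determine the degree of surgically induced astigmatism of femtosecond laser clear corneal incisions". No endpoint in 1.2 or 1.3 is specific to the incision.

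The cohort is defined by AK. Section 3.1 admits "Patients who are planned to undergo femtosecond laser-assisted cataract surgery with astigmatic keratotomy" and adds that "Subjects with planned single or bilateral cataract eye surgeries are eligible". Section 7.3 describes participation "through their femtosecond laser-assisted cataract surgery with astigmatic keratotomy on both eyes". No group without AK is planned.

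On the surgery days (7.2.2 and 7.2.3) the study collects the "various laser parameters that are used to make the astigmatic keratotomies and clear corneal incisions". The only post-operative measurement is at the month 1 visit (7.2.4): "One-month post-operative IOL master, autorefraction, manifest refraction, and uncorrected visual acuity will be collected".

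Section 8.3 names two analyses: "Mean change in keratometric astigmatism will be determined by subtracting preoperative astigmatism from postoperative mean astigmatism", and "Vector analysis and double-angle plot will be used to analyze aggregate astigmatism". It also says that a statistician's help will be needed. The one other analysis mentioned is a regression in 7.1. Its purpose is the nomogram, and its terms are not given.

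**The concern.** Two corneal procedures are done before the single re-measurement, and one of them, the AK, is meant to change astigmatism. The pre-to-post change therefore belongs to the pair. Objective 1 asks about one member of the pair, and the plan does not say how the two will be told apart.

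Either Objective 1 goes unreported, or a whole-operation figure is reported in its place. Such a figure could be too high or too low, depending on where the incisions were placed relative to the steep axis, and it would not be zero even if the incision had no effect. Objective 4 is also exposed: if the nomogram regression leaves the incision out, part of the incision's effect may be credited to the AK.

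**Working it through.** **The plan's own figure.** Section 8.2 gives 20% of 300 eyes: 0.20 × 300 = 60, which reproduces. The same mix gives 150 against-the-rule (ATR) and 90 with-the-rule (WTR) eyes. The point does not depend on these counts, but the mix is used below.

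**What the aggregate vector estimates.** In double-angle coordinates, take an eye with its incision at meridian φ (effect c) and its AK at meridian θ (effect k):

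induced vector = −c(cos 2φ, sin 2φ) − k(cos 2θ, sin 2θ) + error.

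Averaging over eyes gives c times the mean incision direction plus k times the mean AK direction. This has length c if all incisions share one meridian and the AK directions cancel. The 8.2 mix is not balanced, so they need not cancel.

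**Inputs.** From the documents: 300 eyes, 50/30/20% ATR/WTR/oblique (8.2). Assumed, because the documents give none of these:
- c = 0.30 D and k = 0.80 D;
- measurement error SD 0.15 D per component, before and after;
- AK on the measured steep axis;
- steep axes uniform within 30 degrees of 180 (ATR) or 90 (WTR), with oblique axes spread evenly in between.

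**AK part.** The mean of cos 2θ over ±30 degrees is sin 60° ÷ (π/3) = 0.866 ÷ 1.047 = 0.827. ATR and WTR point in opposite directions and oblique averages to zero, so the mean AK direction has length (0.50 − 0.30) × 0.827 = 0.165. The AK contributes 0.80 × 0.165 = 0.132 D to the centroid.

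**Centroid for a true incision effect of 0.30 D (last row: no effect).**

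| Incision position | By hand | Simulated mean |
|---|---|---|
| 180 degrees | 0.30 + 0.132 = 0.432 | 0.43 |
| 90 degrees | 0.30 − 0.132 = 0.168 | 0.17 |
| 135 degrees | √(0.30² + 0.132²) = 0.328 | 0.33 |
| steep axis | (0.30 + 0.80) × 0.165 = 0.182 | 0.19 |
| half 180, half steep | 0.15 + 0.15 × 0.165 + 0.132 = 0.307 | 0.31 |
| any, no incision effect | 0.132 | 0.14 |

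Simulated values can sit slightly higher because random scatter lengthens an averaged vector.

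**Sensitivity.** For k from 0.4 to 1.2 D (c = 0.30 D), the simulated centroid runs from 0.37 to 0.50 at 180 degrees, 0.24 to 0.12 at 90, 0.31 to 0.36 at 135 and 0.12 to 0.25 on the steep axis. By the hand formula, the half-and-half layout goes from 0.15 + 0.025 + 0.4 × 0.165 = 0.24 to 0.15 + 0.025 + 1.2 × 0.165 = 0.37, so its good agreement is particular to k = 0.80.

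**Post-minus-pre change.** The simulated mean is −0.79, −0.70, −0.74 and −1.04 D for 180, 90, 135 and steep axis, against −0.78 D with no incision effect. At 180 degrees an incision of 0.30 D shifts this mean by about 0.01 D, so it carries almost no information on Objective 1 there.

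**Can the incision be separated?** A regression of each eye's vector on an incision term and on AK terms (a constant and arc length, by astigmatism type) averaged 0.27 to 0.33 D for a true 0.30 D. This covered 180, 90, 135 and half-and-half placement, error SDs of 0.10 to 0.25 D, and AK effects equal or differing by type. If every incision lies on the AK meridian, the incision column equals the sum of the AK constants and the model cannot be fitted. With incisions scattered around the AK meridian with SD 5, 10 or 20 degrees, the SE is about 0.07, 0.04 or 0.02 D. These runs treat eyes as independent; clustering would widen the SEs.

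**The case against.** Section 8.3 never says that either analysis answers Objective 1. The post-minus-pre change fits Objective 2 and the WTR/ATR endpoints in 1.3, and the vector sentence is too brief to show that a cohort centroid will be reported as the incision effect. Incision parameters are collected, a regression is planned and a statistician is to be involved, so the route is undeveloped rather than closed. The illustration rests wholly on assumed inputs, and in two of the five layouts the centroid is near the truth.

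Most of this stands, and it rules out several stronger readings that a reader might infer:
- That the plan will report the combined figure as the incision effect. The text does not say so.
- That the cohort cannot yield the incision effect. Laser parameters for both procedures are recorded, so it may be estimable.
- That the nomogram is biased. The terms of the 7.1 regression are not stated, so this is a risk only.
- That every operated eye has AK. The 3.1 criterion is written per patient. Section 7.3 supports AK in both eyes, but 3.1 does not expressly exclude a fellow eye without it; in any case no analysis of such eyes is planned.

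The objection does not supply an analysis. A future statistician's involvement leaves the method open, and the choice should be made before results are seen.

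**Conclusion.** The gap is real and should be fixed. Objective 1 has no stated analysis that isolates its quantity, and the analyses that are stated measure incision plus AK. This follows from the text and needs no assumption.

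The size of the error, if the aggregate vector were used, depends on inputs that the documents do not give. Under those assumed here, a true 0.30 D could appear as anything from 0.17 to 0.43 D, and a true zero as about 0.14 D. The figure is not always wrong: 135 degrees and the half-and-half mix come out close. The regression is unbiased or nearly so on average in the layouts tested, but that does not guarantee any single study. At an SE of 0.07 D the 95% half-width is 1.96 × 0.07 = 0.14 D.

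**What to change.** In 8.3, state that Objective 1 will be estimated by regressing each eye's induced-astigmatism vector (post minus pre, double-angle x and y) jointly on an incision term along the incision meridian and AK terms along the AK meridian. The AK terms are a constant and arc length, by astigmatism type, because 8.2 expects the types to respond differently. Cluster standard errors by patient, since 3.1 admits bilateral surgery. Report the incision term with its 95% CI, and keep it in the 7.1 nomogram regression.

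The AK constant should not be dropped. Arc length is likely to follow the measured pre-operative astigmatism, which is also subtracted to form the outcome. In simulation with every incision on the steep axis, one AK slope and no constant, the model returned 0.13 D for a true 0.30 D (error SD 0.15 D). With the constant it cannot be fitted, so the problem is visible.

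Confirm that both meridians are among the recorded laser parameters; 7.2 does not list them. If they are not recorded, or incision position does not vary relative to the AK meridian, restate Objective 1 as the combined incision-plus-AK effect. A fixed incision meridian is acceptable if AK meridians vary. The post-minus-pre change can stay as the description of the whole procedure.

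The cost is analysis wording and one check of data capture; no treatment changes. The estimate becomes model-based: it assumes additive effects, the same incision effect at every position, and an AK response linear in arc length within type. AK terms by type cost some precision (SE 0.019 against 0.013 D at 180 degrees), and precision falls further when incisions lie near the AK meridian.

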1.2 Primary Study Endpoints

The primary outcome measures are as follows (collected at post-operative month one):

- Uncorrected visual acuity
- Post-operative corneal curvature measurements and astigmatism as assessed using optical biometer
- Post-operative auto-refraction

1.3 Secondary Study Endpoints

The secondary outcome measures are as follows (collected at post-operative month one):

- Mean change in astigmatism in eyes with ‘with the rule’ (WTR) astigmatism
- Mean change in astigmatism in eyes with ‘against the rule’ (ATR) astigmatism
- Complications related to placement of femtosecond laser AKs

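### AK complications have month one as their only stated collection time and appear in no visit's data list, so early resolved events could be missed and the reported rate biased downward

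*Combined protocol and SAP*

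**What the plan says.** Section 1.3 lists "Complications related to placement of femtosecond laser AKs" among the secondary endpoints. The lead-in to that list gives a single time point: "The secondary outcome measures are as follows (collected at post-operative month one".

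Section 7.2 sets out the data for each visit:

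- Visit 1 (7.2.1), besides demographics and baseline characteristics: "Pre-operative biometry, refraction, and corneal hysteresis data will be collected".
- Visits 2 and 3, the surgery days (7.2.2 and 7.2.3): "Data from the femtosecond laser will be collected, including the various laser parameters that are used to make the astigmatic keratotomies and clear corneal incisions".
- Visit 4 (7.2.4): "One-month post-operative IOL master, autorefraction, manifest refraction, and uncorrected visual acuity will be collected".

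No study visit falls between an eye's surgery and month one except, in bilateral patients, the other eye's surgery day. Section 7.2.4 dates the last visit as "Visit 4 or post-operative month #1 visit (1 month after 2nd operative procedure", and section 3.1 adds: "Planned opposite eye surgery must be within 2-4 weeks of first cataract surgery".

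Section 8.3 removes from the final analysis any eye whose final best-corrected acuity is worse than 20/40. It gives no definition, denominator or summary for complications.

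**The concern.** The endpoint concerns the placement of the incisions, which happens on the day of surgery, but its stated collection time is a month or more later. An event that arises at surgery and clears within weeks need not be visible at that visit, and no visit's list asks for it. At the other extreme, an eye with a lasting complication that keeps acuity below 20/40 could be removed by the analysis rule. Both would lower the reported complication rate. A low or zero count could then reflect how events were looked for rather than how often they occurred.

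**Working it through.** **Plan's own figure.** The plan states no complication rate or precision, so there is none to reproduce. The only related figure is in section 8.2: 0.20 × 300 eyes = 60, which is correct. It is used here only as the source of 300 eyes.

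**Step 1: endpoint against data lists.**

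| Visit | Data named in 7.2 | Complications named? |
|---|---|---|
| 1, pre-operative | demographics, baseline characteristics, biometry, refraction, hysteresis | no |
| 2, surgery | laser data and parameters | no |
| 3, surgery on the other eye | laser data and parameters | no |
| 4, month one | IOL master, autorefraction, manifest refraction, uncorrected acuity | no |

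**Step 2: other routes.** Section 19.1 covers IRB reporting of harms that are both unexpected and probably due to research procedures. Section 7.1 says that all enrolment adds is hysteresis and biometry at month one, so the AK itself is usual care. Section 10.0 has no safety monitoring plan, and section 11.0 lists only loss of confidentiality. None of these states a route for the endpoint.

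**Step 3: time from surgery to Visit 4.** One month is 30.4 / 7 = 4.34 weeks.

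- Second eye: 4.34 weeks. The same is assumed for the only eye of a one-eye patient, since 7.2.4 dates the visit from a second procedure.
- First eye of a bilateral patient: 2 + 4.34 = 6.34 weeks to 4 + 4.34 = 8.34 weeks.

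A literal month-one collection therefore has a longer blind interval for first eyes, and the interval differs between the two eyes of one patient.

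**Step 4: the acuity rule.** If the rule in 8.3 is applied to the complication rate, an eye that stays below 20/40 because of a complication leaves both numerator and denominator. Removing an event from both lowers the rate, so this acts in the same direction as Step 3.

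**Step 5: illustration only.** Assume a true rate p of 1%, 2% or 5% and a share c of events still visible at month one of 25% to 75%. Neither is in the documents. Treat 300 eyes as independent.

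Expected events = 300p. Expected seen = 300pc. Chance of recording none = (1 − pc)^300.

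| p | Expected events | Seen, c = 25% to 75% | Chance of none recorded, c = 25% to 75% | Same, c = 100% |
|---|---|---|---|---|
| 1% | 3 | 0.75 to 2.25 | 0.472 to 0.105 | 0.049 |
| 2% | 6 | 1.5 to 4.5 | 0.222 to 0.011 | 0.002 |
| 5% | 15 | 3.75 to 11.25 | 0.023 to below 0.001 | below 0.001 |

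A count of 0 in 300 would be read as a one-sided 95% upper limit of 1 − 0.05^(1/300) = 0.99%. If the true rate were 2% and only a quarter of events were visible, a zero count would occur about 22% of the time, and the 0.99% limit would then lie below the truth.

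The denominator is not settled either. Section 8.1 gives 300 subjects and section 8.2 uses 300 eyes. Section 3.1 admits bilateral patients, whose two eyes are not independent.

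**The case against.** The strongest reply is that a collection time is not an exclusion rule. Section 1.3 says when outcomes are gathered; it does not limit complications to those present on that day. Recording at month one everything since surgery would fit the words, and section 7.1 describes a look back after that visit, although the effects it names are on astigmatism.

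The lists in 7.2 are also not exhaustive. The surgery-day entry uses an open form, "Data from the femtosecond laser will be collected, including the various laser parameters". The Visit 4 entry omits the hysteresis measurement that 7.1 places at that visit. Section 9.0 refers to a data plan form that is not part of these documents.

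These points stand, and they rule out several readings that a reader might infer:

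- That the plan excludes resolved events, or that nothing can feed the endpoint. The documents show only that no step is stated.
- That all 3 to 15 events in the illustration would be lost. This would need assumed rates of 1% to 5% and no capture at all, not even from the chart.
- That most AK complications occur early. The documents give no timing.
- That the nomogram would be published with an unsupported safety claim. No objective in section 1.1 concerns safety, and no such claim is planned.
- That the narrow scope of 19.1 shows that endpoint data go unrecorded. That section governs IRB reporting, not endpoint collection.

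The reply does not supply a window, a source or a denominator. A cumulative chart review is compatible with the text but is nowhere stated as the plan for complications, and the 20/40 rule is stated with no exception for them.

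**Conclusion.** The concern holds in a limited form. Two stated rules, the month-one collection time and the 20/40 exclusion, can each lower the reported complication rate, and no visit's data list counters them. Early resolved events could be missed; the documents do not show that they would be. The gap is about 4.3 weeks for second eyes and 6.3 to 8.3 weeks for first eyes of bilateral patients.

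The direction of the bias rests on two assumptions: that some complications resolve before Visit 4 or leave acuity below 20/40, and that the plan is followed literally. Its size is unknown. The figures in Step 5 show what assumed inputs would imply and are not estimates. The primary endpoints and the nomogram are unaffected. The amendment is worth making for a secondary endpoint, and does not call the main design into question.

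**What to change.** Make three text changes, ideally before enrolment, because events not recorded in a consistent form are hard to recover later.

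1. Section 1.3: set the complication window per eye as from surgery through the month-one visit.
2. Sections 7.2.2, 7.2.3 and 7.2.4: add a per-eye AK-complication item, filled from the operative note and chart.
3. Section 8.3: state that the complication rate is reported over all operated eyes and that the 20/40 exclusion does not apply to it.

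The cost is one extra form line at visits that already take place, with no new procedure and no change to care. The downside is that the reported rate may look less favourable.

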2.0 Background

2.1 Scientific Background and Gaps

- 1.1. Nearly 20% of people undergoing cataract surgery have significant corneal astigmatism (1.5 D or greater). Patients increasingly expect spectacle independence after cataract surgery, which requires correction of this astigmatism. Femtosecond laser astigmatic keratotomies (AKs) can be used to treat corneal astigmatism, but there are no nomograms developed to guide surgeons on the parameters (i.e. depth and arc length) to use to correct specific amounts of astigmatism. Instead, surgeons must rely on old nomograms that were developed for manual incisions and adapt them for use with the laser.

A well-validated nomogram exists for determining location and arc length of limbal relaxing incisions (LRI), another type of refractive procedure used to treat astigmatism.¹ This calculator specifically states that it is “intended to support the use of LRIs only, it is not intended for the calculation of femtosecond laser incisions.¹”

If we could accurately determine the effect femtosecond laser performed AKs have on corneal astigmatism at the time of cataract surgery, a nomogram to be used specifically with the laser could be reverse engineered.

2.2 Previous Data

One previous prospective study has been published evaluating the effectiveness of femtosecond laser corneal relaxing incisions in reducing corneal astigmatism during cataract surgery.² This study also proposed a preliminary nomogram based on the 51 eyes that were included in the study.² While this study is a landmark paper in proposing a nomogram for AKs, the authors conclude that further study is required to refine and validate the nomogram. In addition, the role of corneal biomechanics, such as corneal hysteresis is not factored into their nomogram. Another study demonstrated that corneal biomechanical parameters are independent predictors of the efficacy of femtosecond laser AKs.³

2.3 Study Rationale

The purpose of this study is to build upon the existing literature to create a nomogram based on a large number of eyes that may be utilized to accurately predict location and arc length of AKs to minimize post-operative astigmatism. This nomogram will incorporate corneal biomechanics, including corneal hysteresis.

3.0 Inclusion and Exclusion Criteria

3.1 Inclusion Criteria

- Age: ≥18 years of age
- Sex: male or female
- Patients who are planned to undergo femtosecond laser-assisted cataract surgery with astigmatic keratotomy at the Schein Ernst Mishra Eye clinic within the next 60 days of their cataract consultation visit. Subjects with planned single or bilateral cataract eye surgeries are eligible. Planned opposite eye surgery must be within 2-4 weeks of first cataract surgery.
- Fluent in written and spoken English

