7.0 Study Design and Procedures

7.1 Study Design

This is a prospective cohort study of patients who are undergoing femtosecond laser-assisted cataract surgery with astigmatic keratotomy. Patients will be selected to participate in the study based on inclusion/exclusion criteria.

It should be noted that this is an observational, not interventional study. The parameters to be chosen for the femtosecond AKs will be determined using best practices (surgeon's choice using algorithms created for manual LRIs but adapted for use with the laser). Whether a patient is enrolled in the study or not will not influence the architecture or plan for the femtosecond AKs. The purpose of the study is to carefully examine the effects of these femto AK on corneal astigmatism in a retrospective fashion (after the 1 month post-operative visit) so that a nomogram can be developed using regression analysis. As such, the only 'intervention' patients enrolled in the study will receive that un-enrolled patients will not is measurement of corneal hysteresis and corneal biometry at their 1 month post-operative visit.

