8.0 Subject Numbers and Statistical Plan

8.1 Number of Subjects

300

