8.2 Sample size determination

Eyes may have with-the-rule, against-the-rule, and oblique astigmatism. Corneas with varying forms of astigmatism will respond differently to the AKs; thus it is necessary to have a sufficient number of eyes to produce results for all forms of astigmatism. Approximately 50% of eyes have against-the-rule astigmatism, 30% with-the-rule, and 20% oblique. 20% of 300 eyes = 60, which was felt to be the minimum number to produce meaningful results for this group.

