16.2 Feasibility of recruiting the required number of subjects

The study team has access to approximately 10-20 potential subjects per week. At a minimum, 25% of subjects (4-5 per week) would need to be recruited in a one year period to reach the required number of participants for the desired study power.

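### Fellow eyes of the same patient enter the data with no stated method for pairing, and the target of 300 is headed as subjects but counted as eyes

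*Combined protocol and SAP*

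**What the plan says.** On enrolment, section 3.1 states: "Subjects with planned single or bilateral cataract eye surgeries are eligible". Section 7.2.3 collects laser data at surgery on the contralateral eye, and the last visit in 7.2.4 is timed from the second operation: "Visit 4 or post-operative month #1 visit (1 month after 2nd operative procedure". Section 7.3 goes further and describes participation "through their femtosecond laser-assisted cataract surgery with astigmatic keratotomy on both eyes", as if every subject were bilateral. Paired eyes will therefore be in the data, but their share is not stated.

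On the unit, the secondary endpoints in 1.3 are mean changes in eyes, and 8.3 drops eyes (not patients) that miss its final acuity threshold. The number 300 stands under the heading "8.1 Number of Subjects", while 8.2 reasons: "20% of 300 eyes = 60, which was felt to be the minimum number to produce meaningful results for this group". Section 16.2 speaks of subjects and participants: "25% of subjects (4-5 per week) would need to be recruited in a one year period to reach the required number of participants".

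On analysis, 8.3 names mean change in keratometric astigmatism, vector analysis and a double-angle plot, and says that a statistician's assistance will be needed. Section 7.1 says the effects will be examined "so that a nomogram can be developed using regression analysis". Objective 3 in 1.1 is "To determine the role of corneal biomechanics (hysteresis) on AK calculations". No section mentions correlation between fellow eyes, a mixed model, GEE, clustered errors, a one-eye-per-patient rule or a design effect.

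**The concern.** Two eyes of one person share anatomy, surgeon and healing, so their residuals may well correlate. An analysis that counts 300 eyes as 300 independent observations then misstates its own precision. Two results are exposed: the mean change, including the vector components, and the judgement on hysteresis. Hysteresis is measured in both eyes of the same person and is likely to be similar in the two. The nomogram has a related exposure. If it is validated by splitting eyes at random, one eye of a pair can sit in the training set and the other in the test set.

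The unit of 300 matters for a different reason. It fixes how many people must be recruited, how many eyes will be available, and whether 60 oblique eyes is the expected yield or only a lower figure.

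**Working it through.** **The plan's own figure.** 0.20 × 300 eyes = 60 oblique eyes. This reproduces. There is no alpha, power, effect size or SD behind 300, so no power formula can be run.

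**The unit.** If a share b of subjects is bilateral, eyes = subjects × (1 + b).

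| Bilateral share b | Subjects if 300 = eyes | Eyes if 300 = subjects | Oblique eyes (20%) if 300 = subjects |
|---|---|---|---|
| 0 | 300 | 300 | 60 |
| 0.5 | 200 | 450 | 90 |
| 1 | 150 | 600 | 120 |

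**Recruitment (16.2).** 4 × 52 = 208 and 5 × 52 = 260 subjects a year.
- If 300 means subjects, 300/52 = 5.8 per week is needed, so 4 to 5 falls short.
- If 300 means eyes, 200/52 = 3.8 per week suffices at b = 0.5, and 150/52 = 2.9 at b = 1. With no bilateral patients 5.8 is needed again.
- The rate is itself loose: 25% of 10 to 20 per week is 2.5 to 5, not 4 to 5.

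**Effect of ignoring pairing.** The inputs that the documents do not give are assumptions: p, the share of eyes that belong to a pair (0 to 1); r, the residual correlation between fellow eyes; and rx, the between-eye correlation of hysteresis (0.8 in the table).

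- Mean: D = 1 + p·r. Actual coverage of a nominal 95% interval = 2Φ(1.96/√D) − 1.
- Hysteresis slope: D = 1 + p·rx·r. Actual rejection rate of a nominal 5% test = 2[1 − Φ(1.96/√D)].

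| p | r | D (mean) | Coverage | Slope rejection (rx = 0.8) |
|---|---|---|---|---|
| 0 | any | 1.00 | 95.0% | 5.0% |
| any | 0 | 1.00 | 95.0% | 5.0% |
| 0.613 | −0.3 | 0.82 | 97.0% | 3.4% |
| 0.613 | 0.5 | 1.31 | 91.4% | 7.9% |
| 0.613 | 0.7 | 1.43 | 89.9% | 9.1% |
| 1 | 0.5 | 1.50 | 89.0% | 9.8% |
| 1 | 0.7 | 1.70 | 86.7% | 11.7% |

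The value p = 0.613 is one illustration. If 208 subjects supply 300 eyes, 300 − 208 = 92 of them have two eyes, and 184/300 = 0.613. It is not a bound. If rx is 0, the slope test stays at 5% whatever r is.

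**Check by simulation.** With 300 eyes from 208 or 260 patients, rx = 0.8 and r from 0 to 0.7, eye-level results agreed with the formulas to within about one percentage point. Patient-clustered errors gave coverage of about 94 to 95% and slope rejection of about 5 to 6%. Subgroups as small as 60 eyes were not simulated.

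**The case against.** The strongest reply has four parts.

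- *No wrong method is specified.* The plan states no alpha, interval or hysteresis test, and it says a statistician will be involved. This stands: the defect is an unspecified method. It does not remove the point. Objective 3 asks for a judgement on a predictor, 16.2 invokes a desired power, and the only unit the plan works in is the eye.
- *The size rests on assumptions.* This stands too. Neither the correlation nor the bilateral share is in the documents. For hysteresis the relevant correlation is that of residuals after arc length and other predictors, which may be lower than the raw correlation. For predictors that differ between fellow eyes the effect can shrink or reverse.
- *The recruitment rate could be used to narrow the range.* Taking 4 to 5 per week as exact would put 27 to 61% of eyes in pairs (80/300 to 184/300). A reader might infer those limits, but the text does not support them. Section 16.2 calls the rate a minimum, its own percentage gives 2.5 to 5, and 7.3 reads as if all subjects were bilateral. Pairing has to be left open from 0 to 100%.
- *The study may be large enough anyway.* If 300 means subjects and all are bilateral, 600 eyes carry the information of 600/1.9 = 316 to 600/1.3 = 462 independent eyes at correlations of 0.9 to 0.3. That is above 300. This is correct for that reading, and it shows why the unit has to be stated.

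**Conclusion.** Two things are certain from the text: no section provides for fellow-eye pairing, and 300 carries two different units. The consequence for precision is conditional. With all eyes paired, eye-level 95% intervals for a mean would cover about 89% at correlation 0.5 and 87% at 0.7. A 5% hysteresis slope test would reject about 9.8% and 11.7% of the time, if hysteresis correlates 0.8 between eyes. With no pairing or zero correlation there is no effect, and with negative correlation the intervals are too wide.

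Three stronger conclusions might be drawn, and the documents support none of them.

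- *That the study is underpowered.* No power value is given, and 60 oblique eyes is offered only as a number felt to be the minimum, so no power claim is shown wrong.
- *That the nomogram or mean change is biased.* Ignoring pairing affects the stated precision, and it does not in itself bias the estimates.
- *That 16.2 is a separate recruitment shortfall.* The shortfall exists only if 300 means subjects, so it is a consequence of the unit conflict.

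The change should be made: the omission is clear and the remedy is cheap, although the gain is small if few eyes are paired.

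**What to change.** In 8.3, state that:

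- mean change, vector components and the nomogram regression use all eligible eyes with the patient as the cluster, by GEE or cluster-robust standard errors (valid for either sign of correlation), with a small-sample correction in small subgroups such as the oblique group;
- any bootstrap or cross-validation of the nomogram resamples by patient, so that fellow eyes stay together;
- the numbers of patients and of eyes are both reported for each analysis.

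In 8.1 and 8.2, state one unit for 300 and the expected bilateral share. Restate 16.2 in that unit, with a weekly rate that agrees with its own percentage, and reconcile the both-eyes wording of 7.3 with the eligibility of single-eye patients in 3.1.

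The cost is a few sentences. No new data or enrolment is needed, since both eyes are already collected within enrolled subjects. The usual price is somewhat wider intervals.
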